7.7 Computerized Edit Checks

The database will incorporate the needed programmed edit checks to help ensure quality data. Messages to the parent may be generated automatically to alert him/her to any entry error or protocol non-compliance.

8. Statistical Analysis

8.1 Sample Size Calculations

A sample size of 40 subjects is estimated under the following considerations:

- Descriptive summary statistics for the categorical and quantitative data will be reported
- Expected dropout rate of ≤10 subjects (if the dropout threshold of 10 is reached,
 up to 10 additional participants may be replaced at the sponsor's discretion)
- A subject will be considered to have dropped out if they are determined to be non-compliant; however, qualifying chatbot interactions will be included in ITT.

8.2 Datasets to be Analyzed

8.2.1 Intent-to-treat (ITT)

All enrolled participants in accordance with the Intent-to-treat (ITT) principle.

8.2.2 Full Analysis Set (FAS)

All ITT participants who have completed at least one topic (Sleep, Stress, and/or Nutrition).

8.2.3 Per Protocol (PP)

All FAS participants who have no protocol violations (i.e. participants who have completed at least seven interactions – protocol deviations are permitted and reportable) and remained in the study for the full data collection period.

Protocol violations and deviations and study completion data will be evaluated through statistical analysis.

8.3 Primary Endpoints

This study's primary objective is to generate real-life, in-home data from parents with infants (preterm and full-term) on sleep, stress, and infant nutrition via the study chatbot. The primary endpoint(s) are records of sleep, stress, and infant nutrition from parents of infants (preterm and full-term) through interaction with the study chatbot.

8.4 Secondary Endpoints

The study's secondary objective is to investigate differences in data obtained from parents of preterm infants versus data obtained from parents of full-term infants on sleep, stress, and infant nutrition.

In order to evaluate these differences, data obtained through RQDA (see 8.3.1 above) will be categorized in order to develop outcomes and/or measures that can be analyzed between groups. The exact nature of these secondary endpoint variables is unclear as of the development of this SAP; however, said variables will be established in a written agreement with Danone's Chatbot team.

Tables, listings, and figures pertaining to secondary endpoints are grouped by analysis data set (FAS and PP) in the TLF shells.

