Tables 6-11 report open-ended answers to questions 9, 10, 11, 12, 13, and 14 of the Usability of Chatbot and ClaimIt eQuestionnaire. As nearly all answers to open-ended questions will be unique, all answers of a like theme will be recorded (for all intents as purposes) as the same answer. For example, if one respondent answers question 13 ("What did you like the most about the ClaimIt app?") by saying "I thought the app was easy to use", another answers "Easy to use", and another answers "Ease of use", then this answer will be reported as "Easy to use" (for example) with a frequency of three

(3). Any answers that are completely unique will be reported as such with a frequency of one (1).

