10.1 Clinical Study Report

A Clinical Study Report will be developed and provided by ObvioHealth after the following have occurred: database lock, completed statistical analysis, and completed and client-approved TLF deliverable (through executed Tables, Listings, and Figures Deliverable Finalization Form). The report will review study background and methodology and will include all required results including all tables, listings, and figures agreed upon in the TLF Deliverable Shell (see Section 10.2 immediately below).

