10.2 TLF Deliverable Shell

In conjunction with the finalized SAP, ObvioHealth and Danone will agree upon a set of tables, figures, and listings that will be provided as part of the final study deliverable – the TLF Deliverable Shell.

The TLF Deliverable Shell will consist of a set of spreadsheets (or in other words, a workbook) that houses the empty versions of all tables and listings for this study. The final worksheet in this workbook will be a list of figures to be delivered.

An executed SAP constitutes a written agreement on the TLF Deliverable Shell. As such, the most recent TLF Deliverable Shell will be versioned to 1.0 and considered final. Any additions to the final TLF Deliverable Shell after execution will require an amendment to the SAP and potential changes to the study contract.

11. References

- World Health Organization. (2017). Preterm birth. 2017 November [Accessed February 2, 2018]; Fact Sheet. Available from: http://www.who.int/mediacentre/factsheets/fs363/en/.
- 2. Fletcher, L., et al. (2017). *Parental Perception of Risk Associated With Their Premature Infant*. Adv Neonatal Care, 2017. **17**(4): p. 306-312.
- 3. Mughal, M.K., et al. (2017). *Parenting stress and development of late preterm infants at 4 months corrected age*. Res Nurs Health, 2017. **40**(5): p. 414-423.
- 4. Gondwe, K.W., et al. (2017). *Maternal Psychological Distress and Mother-Infant Relationship: Multiple-Birth Versus Singleton Preterm Infants*. Neonatal Netw, 2017. **36**(2): p. 77-88.
- 5. Polic, B., et al. (2016). Late preterm birth is a strong predictor of maternal stress later in life: Retrospective cohort study in school-aged children. J Paediatr Child Health, 2016. **52**(6): p. 608-13.
- 6. Rahman, A. M., Al Mamun, A., & Islam, A. (2017). Programming challenges of chatbot: Current and future prospective. *Humanitarian Technology Conference* (R10-HTC), 2017 IEEE Region 10: p. 75-78.

12. Appendices

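### The preterm versus full-term comparison variables are still to be built from coded transcripts, with no operational merging rule, no masking of coders to group, and no date before group data are seen

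*SAP*

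**What the plan says.** The secondary objective is the study's only between-group objective. For it, SAP 8.4 says that "data obtained through RQDA (see 8.3.1 above) will be categorized in order to develop outcomes and/or measures that can be analyzed between groups". It then says "The exact nature of these secondary endpoint variables is unclear as of the development of this SAP", and adds that "said variables will be established in a written agreement" with the sponsor's chatbot team. No date, database-lock link or data-access condition is attached to that agreement.

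On coding, SAP 8.4.1 leaves word pairings and coding schemes to the RQDA user. SAP 8.7.1 says of open answers to the usability questionnaire that "all answers of a like theme will be recorded (for all intents as purposes) as the same answer". It gives one example, about ease of use, and lists wholly unique answers with a frequency of one. SAP 8.7.2 carries the same approach to Tables 12-28, the open questions in the chatbot scripts, and stratifies script results by gestational maturity when they are presented.

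Three passages work as safeguards:

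- SAP 8.4: "Tables, listings, and figures pertaining to secondary endpoints are grouped by analysis data set (FAS and PP) in the TLF shells".
- SAP 10.2: "An executed SAP constitutes a written agreement on the TLF Deliverable Shell". Later additions to the shell "will require an amendment to the SAP and potential changes to the study contract".
- SAP 10.1: the study report "will include all required results including all tables, listings, and figures agreed upon in the TLF Deliverable Shell".

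**The concern.** If the person who decides which answers belong to one theme, or which themes become comparison variables, can see which families are preterm, those decisions can follow the contrast instead of preceding it. This need not be deliberate. A borderline answer is easier to place when one already has a picture of how the groups differ.

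No hypothesis test is planned, so no error rate is at stake. What is at stake is whether the description of the secondary objective can be trusted. With 20 families per group and one answer each, moving one family's answer into or out of a theme shifts that group's share by 1/20 = 5 percentage points. A reader of the report could not tell a real contrast from one shaped by the merging.

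**Working it through.** **1. What is fixed and what is open.** The plan gives no figure on this point to reproduce; the sample of 40 rests on descriptive reporting and expected dropout only. The check therefore starts from the text.

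| Element | Status | Place |
|---|---|---|
| Between-group variables | Unclear; later agreement | SAP 8.4 |
| Timing of that agreement | Not stated | SAP 8.4 |
| Coding scheme | User-defined; none given | SAP 8.4.1 |
| Theme merging | Principle, one example, unique answers listed; no boundary rule | SAP 8.7.1, 8.7.2 |
| Masking of coders, second coder of text, agreement check | None stated | SAP 8.4.1, 8.7, 9.1 |
| Titles of tables and figures | Frozen in the shell when the SAP is executed | SAP 10.2 |
| Access to transcripts | Study team reads them | SAP 7.5 |

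SAP 8.4 and 10.2 do not fit together. If the frozen shell already defined the comparison variables, 8.4 would not need to call them unclear and defer them. If it did not, freezing it cannot define them. The shell is not among the documents, so which of these holds cannot be settled here.

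**2. What merging can reach.** The sleep script (SAP Appendix II) has many pre-coded items: slept well or not, under 7 hours or 7 and over, what affected sleep, what woke the parent, tired or rested, afternoon tiredness, how tiredness was managed, whether that helped, and a 1-4 quality rating. Theme merging does not touch these. It reaches the free-text follow-ups and the open response behind each *other* option. SAP 8.4 names none of the closed items as a secondary variable, so the choice among them is still open.

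**3. Size of the boundary effect (illustration).**

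Inputs from the documents: 20 families per group (SAP 6); up to 10 dropouts (SAP 8.1), taken as evenly split, so 15 per group; at most 12 sessions (SAP 7.1) and at least 7 for a compliant family (SAP 7.3).

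Assumed inputs: no true difference; a core theme at 10-40%; *b* borderline answer types, each at frequency *q*. The documents give no such frequencies.

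Model: each group's answers are multinomial with the same probabilities, and gap = |preterm share − full-term share|. Each borderline type is either in or out of the theme, so there are 2^b possible boundaries. *Label withheld* is the mean gap over all 2^b boundaries. *Group-aware* is the largest gap over them, the upper bound for a coder who always picks the larger contrast.

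One answer per family, 200,000 draws per setting:

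| Borderline types | Label withheld, n = 20 | Group-aware, n = 20 | Rise, n = 20 | Rise, n = 15 |
|---|---|---|---|---|
| 1 at 10% | 8.6-12.4 points | 11.7-15.6 | about 3 | about 3.5 |
| 2 at 5% | 8.7-12.5 | 13.1-17.1 | about 4.5 | about 5 |
| 3 at 10% | 10.5-12.3 | 19.5-21.5 | about 9 | about 10 |

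Parents may answer repeatedly, and averaging over answers shrinks chance gaps. With 7-12 answers per family, 20 families per group, core theme 25% and an assumed within-family correlation of 0.1-0.5, the rises become about 1.3-2.4, 2.0-3.6 and 3.9-7.1 points. A re-run of both versions gave the same rises to within rounding.

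**The case against.** The best defence has four parts.

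*The shell settles it.* Secondary outputs are said to be in the shell, executing the SAP makes the shell final, additions need an amendment, and all agreed outputs are reported. This limits selective reporting of whole tables, and that part stands. It does not say which free-text answers belong to which theme, and SAP 8.4 in the same version still treats the variables as open.

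*Merging comes before the split.* SAP 8.7.2 stratifies at presentation, which suggests that answers are compiled across all families first. That is a fair reading and reduces the concern. It is still not masking: nothing withholds the label from the coder. The review of coding and results in SAP 9.1 concerns mainly program code, not the assignment of answers to themes.

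*Chance dominates anyway.* With one answer per family, the mean gap is about 9-13 points even with the label withheld, so masking will not make small contrasts interpretable. True, but it removes an avoidable addition to that noise which, unlike chance, runs toward a difference.

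*It is a descriptive pilot.* Correct, and this bounds the severity.

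Stronger readings that the documents do not support:

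- A reader might infer from the dates (Protocol V3 31AUG2018, SAP v1.0 08APR2019) and from the daily compliance review in Protocol 10.7 that group data had been seen before the SAP was executed. The date on which recruitment opened is not given, and compliance review is not shown to be sight of themes by group. No timing claim can be made.
- A reader might infer that there is no merging rule at all. There is a principle, an example and separate listing of unique answers; what is missing is an operational boundary.
- A reader might infer an inflated false-positive rate. No test is planned, so there is none to inflate.
- SAP Appendix III (headed as the stress script) and the visible part of Appendix IV repeat the sleep flow. This shows an error in the document, not that the wrong script was given to parents.

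**Conclusion.** The concern holds in limited form and should be fixed. As written, the plan permits group-aware construction of open-text themes and of the SAP 8.4 variables, in the study's only between-group comparison. It does not show that this happened or will happen.

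The size is illustrative: an upper-bound rise in the mean chance gap of about 3-9 percentage points with one answer per family, or about 1-7 points with 7-12 answers, at 20 families per group. This rests on no true difference, assumed borderline frequencies, an assumed within-family correlation for repeated answers, and a coder who always takes the larger contrast. Real behaviour would be milder. Closed items are outside the merging problem. Confidence is medium, because the table shell could narrow the gap and could not be read.

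**What to change.** 1. Do the RQDA coding and theme merging on transcripts pooled across groups, with the preterm/full-term label withheld. Gestational age is collected in the Screening eQuestionnaire (Protocol Appendix I), which SAP 7.2 lists as a source separate from the transcripts, so the label can be left unmerged.
2. Before the label is merged, sign off a codebook with its merging rule and a short list of comparison variables per topic, including existing closed items.
3. Reconcile SAP 8.4 with 10.2, and date the written agreement to that sign-off.
4. Label any contrast defined later as post hoc.

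The cost is one data-handling step, a sign-off and SAP text; no new data. Any output added to the final shell needs an SAP amendment and possibly a contract change. Masking will be partial: some transcripts reveal prematurity, study staff may already have read them, and the monitor checks both transcripts and eCRF data (Protocol 13.1). The coder should therefore be someone outside monitoring where possible.

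Document corrections only, which change no result: the reference in SAP 8.4 to a section 8.3.1 that does not exist (RQDA is in 8.4.1); the pointer in 8.4.1 to RQDA sample output in Appendix III, which is not there; and the sleep script repeated in Appendix III and in the visible part of Appendix IV.

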8.4.1 Qualitative Data Analysis

The RQDA package (housed within the R statistical analysis software) will be used to perform the analysis of the free-text data stream that will be produced from Chatbot. As a background, RQDA is a R package for Qualitative Data Analysis, a free qualitative analysis software application (BSD license). It works on Windows, Linux/FreeBSD and Mac OSX platforms. RQDA is an easy to use tool to assist in the analysis of textual data. At the moment it only supports plain text formatted data. All the information is stored in a SQLite database via the R package of RSQLite. The GUI is based on RGtk2, via the aid of gWidgetsRGtk2. It includes a number of standard Computer-Aided Qualitative Data Analysis features. In addition, it seamlessly integrates with R, which means that a) statistical analysis on the coding is possible, and b) functions for data manipulation and analysis can be easily extended by writing R functions.

RQDA allows the user to define certain word pairings, coding schemes, etc. that can be used to pick out trends within the free text. The user can isolate one free text document or can analyze across as many documents as are necessary. For the

purposes of this study, we will analyze trends within among/between subjects. Sample output for the RQDA package is found in Appendix III.

8.5 Exploratory Endpoints

The study's exploratory endpoint is an evaluation of the usability of ClaimIt, the study chatbot and chatbot tools in general, among this population.

To accomplish this analysis, descriptive statistical analysis will be performed on each question of the Usability of Chatbot and ClaimIt eQuestionnaire. Questions will be analyzed for frequency and, in the case of questions that are based on Likert Scales, univariate distributions (mean, median, standard deviation, etc.).

Question 9 through 14 of the questionnaire are open-ended. Qualitative analysis will be performed on these questions where possible in order to obtain the frequencies of certain response patterns. In the case of individual answers (that do not follow a pattern) such will be presented in list form.

Tables, listings, and figures pertaining to exploratory endpoints are grouped by analysis data set (FAS and PP) in the TLF shells.

8.6 Interim Analysis

No interim analysis is planned.

8.7 Tables, Figures, and Lists

8.7.1. Baseline characteristics and Usability Questionnaire

Tables of outputs from the proposed analysis are detailed in the TLF Deliverable Shell (see Section 10.2 for details). They are described below.

Table 1 outlines the baseline characteristics of both the respondents and infants in question. The mean age for respondents is reported with a standard deviation. Frequencies and percentages are reported for the following age categories: 21-25,

26-30, 31-35, 36-40, 41-45, and older than 45. Gender is reported for respondents as male and female.

Mean age for infants is also reported with standard deviations. Frequencies and percentages are reported for the following age categories: newborn (<1 month), 1 month, 2 months, 3 months, 4 months, 5 months, 6 months. Frequencies and percentages are given for both gestational age categories (premature (<37 weeks) and full-term (\geq 37 weeks)). Gender is also reported for infants as male and female.

Table 2 record the mean and standard deviation of Likert score responses as well as frequencies and percentages for questions 1, 2, 3, 4, 7, 8, 15, and 16 of the Usability of Chatbot and ClaimIt eQuestionnaire. Mean scores and standard deviations are reported as numbers to two decimal places. For example, if thirty of the forty mothers answered question one of the questionnaire as "Very easy" while ten of the participants answered "Easy", then the mean response value for that question would be 4.75 with a standard deviation of 0.44.

Table 3 reports the frequencies and percentages of responses to questions 5 and 6 of the Usability of Chatbot and ClaimIt eQuestionnaire which address whether or not the study chatbot malfunctioned (Yes or No) and whether or not the ClaimIt app malfunctioned. For each software malfunction, the participant is asked to report what happened. Their responses are recorded for all chatbot malfunctions in Table 4 and all ClaimIt malfunctions in Table 5.

Tables 6-11 report open-ended answers to questions 9, 10, 11, 12, 13, and 14 of the Usability of Chatbot and ClaimIt eQuestionnaire. As nearly all answers to open-ended questions will be unique, all answers of a like theme will be recorded (for all intents as purposes) as the same answer. For example, if one respondent answers question 13 ("What did you like the most about the ClaimIt app?") by saying "I thought the app was easy to use", another answers "Easy to use", and another answers "Ease of use", then this answer will be reported as "Easy to use" (for example) with a frequency of three

(3). Any answers that are completely unique will be reported as such with a frequency of one (1).

8.7.2. Analysis of Scripts

A series of analyses will be performed based on the Nutrition, Sleep, and Stress scripts administered to each participant. Results will be presented through figures and tables as appropriate.

Figures 1-21 are listed in the TLF deliverable shell. All figures will be in presented as bar charts and will provide enumerations of the categories detailed in their respective titles. Categorizations and subdivisions within each table are indicated by the word "by" in the title.

Tables 12-28 will present response frequencies to all open-ended questions within the scripts administered to each participant. Answers of the same theme will be compiled and presented as frequencies of the same answer as explained above in the example for Tables 6-11. Again any answers that are completely unique will be listed with a frequency of one (1).

All results from the analysis of chatbot scripts will be stratified by gestational maturity (preterm versus full-term) upon presentation.

9. Quality Control

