Appendix II: Sleep Script

				How did you sl	How did you sleep last night?				
		Good				No	Not well		
Thanks for sharing that. How many total hours of night?	g that. How m	nany total hour night?	s of sleep did you get last	ou get last	Thanks for sh	Thanks for sharing that. How many total hours of sleep did you get last night?	any total ho night?	urs of sleep did	you get last
[Collect open ended numerical response and filter	ed numerical r	esponse and fi	lter into below categories]	:ategories]	[Collect open	[Collect open ended numerical response and filter into below categories]	onse and	filter into below	categories]
<7 hours	>7	≥7 hours	I don't know	know	<7 hours	≥7 hours		I don't know	know
		7	That's ok, I only need an estimate.	nly need an ate.		That is a good amount of	unt of	That's ok, I only need an estimate.	nly need an ate.
i m glad you still reel well-rested. Did anything affect your		I nat Is a good amount of sleep! Did anything bother you	[Collect open ended numerical response]	en ended response]	What do you think affected	sleep. Why do you feel like you didn't sleep well?	u feel p well?	[Collect open ended numerical response]	ded numerical nse]
sleep?		about your sleep?	Please share what may have affected your sleep last night.	what may I your sleep ight.	your steep:	bid anything bother you about your sleep?	nok Ja	Please share what may have affected your sleep last night.	hat may have eep last night.
			[All o	questions lead	[All questions lead to these responses]	[5			
			l woke u	I woke up during the night.	ight.				
I went 1	I went to bed too late.		Sorry to hear how often yo	Sorry to hear that, do you remember how often you woke up? [Collect open ended response]	emember ollect open	I woke up too early.	٠	Other	Nothing affected my
Sorry to hear that, what in particular kept you awake?	what in particu awake?	ular kept you		What wo	What would you say woke you up?	: you up?		What do you	Skip to question
I couldn't get to sleep	My baby	Other	I had to go to the bathroom	My baby	Physical discomfort	I had a lot on my on mind	Other	feel affected your sleep?	below]

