Did it ta more t minutes slee	Did it take you more than 30 minutes to get to sleep?	Please share what happened with your	Please share what kept you		Please share what happened with your baby that kept you up.	Please share what made you feel physically uncomfortable (i.e. too hot, too cold, pain, etc.)	Please share what was on your mind.	Please share what kept you awake.	[Collect open ended response]	
	Yes	baby that kept you up.	awake.			[Collect open ended response]	l response]			
S O	How come?				Was there an	Was there any other reason you may have been awoken?	ı may have be	en awoken?		
					Yes					
) (Collec	[Collect open ended response]	[əsuods:	[Return to "N	Vhat would you above]	[Return to " What would you say woke you up ?" above]		No		
				Did anythin	Did anything else affect your sleep?	ur sleep?				
				Yes						
What e	lse affecte	What else affected your sleep? [Return to "What	eturn to "Wha	rt do you think	affected your sl	do you think affected your sleep?" responses above]	love]	0 Z		
		On a scale of 1	to 4 (1 being	Very Good and	4 being Very B	On a scale of 1 to 4 (1 being Very Good and 4 being Very Bad), how would you rate your quality of sleep last night?	u rate your qu	ality of sleep	last night?	
				1	[Collect open ended response]	ded response]				
			Thanks for		. How did you f	sharing that. How did you feel when you woke up this morning?	up this morr	ing?		
								Other		
	Ē	Tired		Well-rested	sted	How would yo	λυ describe hα	ow you felt wh	How would you describe how you felt when you woke up this morning?	this morning?
							ie [Colle	[Collect open ended response]	response]	
Did you s	still feel tir	Did you still feel tired in the afternoon?		s great! Did you fee afternoon?	That's great! Did you feel tired in the afternoon?	a l	Did you f	Did you feel tired in the afternoon?	e afternoon?	
				[All c	questions lead t	[All questions lead to these responses]				
				Yes					No	

			I'm glad to hear that! Would you like	some additional information on improving sleep quality overall?				No	
ır way?		ua.	Ç	2		I'm sorry to hear that. Would you find it helpful if we shared some additional information on improving sleep quality overall?			with me today!
Did you take a nap or manage being tired in any other way?		ou take? Other [Collect open ended response]			ON N	I'm sorry to hear that. Would me additional information o		proving sleep and sleep althy/510/sleep	Thanks for chatting with me today!

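### SAP 8.7.2 plans only category counts for the chatbot scripts and specifies no numeric summary or preterm versus full-term difference for hours slept or the 1-4 sleep rating

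*SAP*

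**What the plan says.** The secondary objective (SAP 5.2) is to investigate differences between parents of preterm and full-term infants on sleep, stress and infant nutrition.

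SAP 8.7.2 gives the outputs for the scripts. On Figures 1-21: "All figures will be in presented as bar charts and will provide enumerations of the categories detailed in their respective titles". On the tables: "Tables 12-28 will present response frequencies to all open-ended questions within the scripts administered to each participant". On the groups: "All results from the analysis of chatbot scripts will be stratified by gestational maturity (preterm versus full-term) upon presentation". No mean, median, SD, difference, interval or test is named for any script item.

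The sleep script (SAP Appendix II) asks for total hours slept, with the instruction "Collect open ended numerical response and filter into below categories". The categories are under 7 hours, 7 hours or more, and a don't-know branch that then asks for a numeric estimate. Later the script asks for a sleep quality rating, "1 being Very Good and 4 being Very Bad".

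Elsewhere the SAP does specify numeric summaries. In 8.7.1, Table 1 gives mean and SD for parent and infant age, and Table 2 gives mean and SD, as well as frequencies, for the 1-5 usability items.

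**The concern.** Hours slept is collected as a number and is a natural variable for the sleep part of the preterm versus full-term comparison. The 1-4 rating is close in kind to the usability items that do get means and SDs. Yet for the scripts the SAP describes counts only. A reader of the final report could see two bar charts side by side, with no estimate of how far the groups differ and no indication of its precision.

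The groups are small: 20 parents each, or about 15 each if the 10 dropouts allowed for in SAP 6.2.3 fall evenly and are not replaced. If the two script categories became the only form in which hours were reported, precision would be lost that could be kept for almost nothing, and a difference lying wholly on one side of 7 hours would not show. Counts pooled over sessions would also weight parents by the number of sessions they completed, and would invite treating repeated replies as independent.

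**Working it through.** **The plan's own figures.** The sample size of 40 (SAP 8.1) comes with no SD, effect size, alpha or power, so no formula can reproduce or contradict it. The worked example for Table 2 (30 scores of 5, 10 of 4) does reproduce: mean = (30×5 + 10×4)/40 = 4.75; SD = √[(30×0.25² + 10×0.75²)/39] = √(7.5/39) = 0.44.

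**Inputs from the documents.** 20 parents per group (SAP 6); at most 12 interactions per pair (SAP 7.1); 7 or more interactions for a compliant parent (SAP 7.3); hours recorded as a number and filtered at 7 (SAP Appendix II).

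**Assumptions not in the documents.** Hours are normally distributed; a share p of nights falls on one side of 7 hours, p = 0.5 to 0.9; correlation ρ between nights of the same parent, 0.1 to 0.9.

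**Hours, one night per parent.** With c = Φ⁻¹(p), the efficiency of the split relative to the number is E = φ(c)²/[p(1−p)].

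- p = 0.5: 0.3989²/0.25 = 0.637, a loss of 36%
- p = 0.7: E = 0.576, a loss of 42%
- p = 0.8: E = 0.490, a loss of 51%
- p = 0.9: E = 0.342, a loss of 66%

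The median split is the best case. It makes 20 parents worth 0.637×20 = 12.7. For scale only, since the plan specifies no test: at two-sided alpha 0.05, a difference of 0.886 SD has 80% power as a number with 20 per group, 58.6% when split at the median and 46.2% with an 80/20 split.

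**Hours, m sessions averaged per parent.** With total variance 1, the variance of a parent's mean hours is V_num = ρ + (1−ρ)/m. For the parent's proportion of nights, let k = Φ₂(c,c;ρ) − p², the covariance of two nights' indicators. Then V_cut = k + [p(1−p) − k]/m, and E = φ(c)²·V_num/V_cut.

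Example: p = 0.5, ρ = 0.5, m = 12. k = arcsin(0.5)/(2π) = 0.0833; V_num = 0.5 + 0.5/12 = 0.5417; V_cut = 0.0833 + 0.1667/12 = 0.0972; E = 0.1592×0.5417/0.0972 = 0.887, a loss of 11.3%.

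Losses over ρ = 0.1, 0.3, 0.5, 0.7, 0.9:

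| Split | 12 sessions | 7 sessions |
|---|---|---|
| 50/50 | 11.3-21.5% | 15.1-26.3% |
| 70/30 | 16.8-28.1% | 20.8-31.8% |
| 80/20 | 24.7-37.6% | 29.2-39.9% |
| 90/10 | 39.2-54.5% | 45.1-55.5% |

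At ρ = 0 the losses return to the one-night values.

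**The 1-4 rating.** From counts n₁ to n₄ the mean is Σj·nⱼ/Σnⱼ, and the SD follows in the same way. Showing all four counts by group therefore discards nothing of the recorded score. What is absent is the difference between groups and an interval that respects the parent as the unit.

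**The case against.** A reader might infer that the SAP has decided to dichotomise hours at 7. The documents do not support that. Appendix II is a conversation script, and its categories choose the chatbot's next question. No section names them as an analysis variable. The figure titles are in a TLF shell that is not among the documents. The tables of open-ended replies could include raw hours, since the script itself treats hours as an open-ended reply. This objection stands, so the losses above are conditional.

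A reader might also infer that hours will never be compared as numbers. That is not established either. SAP 8.1 says: "Descriptive summary statistics for the categorical and quantitative data will be reported". SAP 8.4 leaves the secondary variables to a later written agreement. But the line in 8.1 is generic and names no variable. Protocol 11.3 assigns descriptive statistics to the two surveys and, for the transcripts, speaks of categorising and tabulating patterns. A deferral is not a specification. Raw hours in a frequency table would still give no group estimate.

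A loss of a third or more might be taken as general. It holds for one night per parent or for an extreme split, not for 7-12 averaged sessions with splits near the middle. It does not apply to the rating at all. Nor can an interval in percentage points be set against one in hours to show the loss, because the scales differ.

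Finally, this is a descriptive pilot whose primary endpoint is obtaining records, and the transcripts are kept, so nothing is irretrievable. That limits the severity. It does not remove the case for stating an estimate for the secondary objective before the data are analysed.

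**Conclusion.** The point holds as a gap in specification. SAP 8.7.2 names only counts and frequencies for the scripts, and no other section supplies a numeric summary or group difference for hours slept or the 1-4 rating, although comparable summaries are specified for age and usability.

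The cost for hours is conditional on reporting them only as below or at least 7, and on normality. It is at least 36% of the information with one night per parent. It is about 11-32% with 7-12 sessions averaged per parent, within-parent correlation 0.1-0.9 and splits from 50/50 to 70/30; with a 90/10 split it reaches 39-55%. The documents give no distribution, SD or within-parent correlation to narrow this. For the rating the loss is nil, and only the estimate and interval are missing.

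The point is confined to the sleep items. In the text available, SAP Appendices III and IV repeat sleep questions, so numeric items on stress or nutrition cannot be judged. It is worth correcting before analysis, but it does not threaten the primary endpoint.

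**What to change.** Keep the numeric replies in the analysis dataset, including the estimates given after a don't-know answer. In SAP 8.4, name per-parent mean hours slept and per-parent mean 1-4 rating as secondary variables. Add one table by group with n, mean, SD, median and range of the parent means, and the preterm minus full-term difference with a 95% CI. Calculate the interval from one value per parent, so that repeated sessions are not treated as independent.

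With 20 per group and equal SDs, the half-width is t(38)×√(2/20) = 2.024×0.3162 = 0.64 times the between-parent SD of those means. That tells readers how little or how much the comparison can show.

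Include the number of awakenings only with a stated rule for nights when that question was not reached, since the script asks it only of parents who report waking in the night. Keep the existing charts, and if hours are shown split at 7, label that as a secondary display.

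The data are already collected. The cost is an SAP amendment and a change to the TLF shell, which under SAP 10.2 may also touch the study contract once the SAP is executed, plus a small amount of analysis work.
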